2.3 STUDY SETTING & TARGET POPULATION

This study targets elementary school students in Zamboanga del Norte. This is a province situated in the region of Mindanao in the Philippines. In 2018, it had a poverty incidence rate of 51.6 percent¹⁴, the highest in the Philippines. UNICEF has designated Zamboanga del Norte a target district for DepEd's national WASH in Schools (WinS) programming for 2020. WinS promotes "correct hygiene and sanitation practices among school children and a clean environment in and around schools" and includes initiatives related to infrastructure, knowledge, and behavior change, but does not include other programs with an explicit focus on handwashing promotion. All schools in the study will have WinS policy implemented.

¹⁴ The Poverty and Human Development Statistics Division. "First Semester 2018 Official Poverty Statistics of the Philippines" (2019). Quezon City: Philippine Statistics Authority.

Pre-analysis plan [DRAFT] | January 20, 2020

Within Zamboanga del Norte, DepEd has identified all school districts within Zone 1-3, and several in Zone 4, as sites for the study. The zones are geography-based organizational clusters that DepEd uses to administrate its schools. DepEd excluded the remaining school districts within the school division due to safety and accessibility concerns. We also excluded schools that were receiving additional WASH-related programming besides WinS. The remaining schools were available for the study, and a subset of them were selected as the sampling frame (see Section 2.5 Recruitment Strategy).

Most DepEd schools have toilets and handwashing facilities within each classroom, so this intervention is designed for those types of facilities. However, for classrooms that do not have in-classroom handwashing facilities, the intervention will also be implemented at group handwashing facilities that are outside but close to these classrooms within the schools. We will specifically target pupils from two sets of grades at the sample schools: pupils from grade 1-3, and pupils from grade 4-6. UNICEF and DepEd had previously noted the importance of understanding the potentially different impact of handwashing interventions on pupil iHWWS in these grade groups, in order to inform future implementation plans.

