2.5 SAMPLE SIZE CALCULATIONS

This study is powered to detect at least 7 percentage points or greater in handwashing rates between treatment and control schools. The minimum detectable effect size (MDES) of 7 percentage points was determined as a policy-relevant benchmark based on IDinsight's conversations with our partner, UNICEF, about school-based handwashing campaigns in the Philippines. In our previous study, handwashing rates in Philippines schools were estimated at around 2 percent. As in our previous studies, a scale-up recommendation to DepEd will require that the program demonstrate improvements to handwashing that move rates beyond the threshold of 15 percent. Therefore, assuming conservatively that the baseline control group handwashing rates among the schools in our sample is 10 percent and the intra-cluster correlation is 0.1^{27} , a sample size of 100 schools in total with MDES of 7 pp provides sufficient power to inform the policy decision above with some buffer.

²² Ibid.

²³ Ram, Pavani K., et al. "Is structured observation a valid technique to measure handwashing behavior? Use of acceleration sensors embedded in soap to assess reactivity to structured observation." *The American journal of tropical medicine and hygiene* 83.5 (2010): 1070-1076.

²⁴ Ibid.

²⁵ Halder, Amal K., et al. "Observed hand cleanliness and other measures of handwashing behavior in rural Bangladesh." BMC Public Health 10.1 (2010): 545.

²⁶ Ram, Pavani. "Practical guidance for measuring handwashing behavior: 2013 update." Water & Sanitation Program: Working Paper (2013).

²⁷ ICC=0.07 from previous HiFive study. We use an ICC of 0.1 as a more conservative estimate, in the event that handwashing outcomes are more correlated within schools in ZDN compared to the provinces (Puerto Princesa and Camarines del Norte) where our previous HiFive took place.

Pre-analysis plan [DRAFT] | January 20, 2020

Provided the true effect of the program is indeed as small as 7 percentage points, a sample size of at least 100 schools with 26 handwashing observations per school enables the experiment to be well-powered, or sensitive enough, to detect a difference of this magnitude or greater with an 80 percent chance of statistical significance.

To buffer against attrition due to safety risks (i.e. not being able to observe a school because the area is deemed unsafe), we expanded the sample size to 132 in total, with 66 schools per arm.

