³⁴ The approach to test the difference in impact of the program for these two sub-samples will be separate regressions for each sub-sample and then a test comparing the treatment effects across the two regressions. This will be performed instead of a single regression on the pooled sample with an interaction term between the treatment term and the sub-sample for the sake of simplicity, as the former approach would require multiple interaction terms for all co-variates, as well as threeway interactions when exploring other sub-groups.

Note on sample weights: Sample weights will be included to account for the fact that the sampling probability of classes for a given grade is different across schools. Since a constant number of classes will be sampled for each grade in each school³⁵, schools with more classes for a given grade will have a lower probability of being selected. This will be accounted for by using weights that represent the inverse probability of class selection. By doing so, each pupil observed or surveyed will have the same probability of inclusion into the sample.

Table 3 below provides a summary of the indicators for this research question, and the unit of analysis and sample corresponding to each indicator. Table lists the co-variates we will use in addition to the indicators in our analytical models to answer research question 1. We will report estimates for our outcome indicators both with and without controls.

³⁵ For classroom observations, one class in each grade in each school will be sampled independent of the total number of classes in the grade.

Pre-analysis plan [DRAFT] | January 20, 2020

Outcome category	Outcome	Metric	Unit	Sample	Analytic model ³⁶ (LPM – linear probability model ; OLS – ordinary least squares)
Independen t	Pupil washed hands with soap and water after toilet use	Y.1 – binary variable for whether pupil was observed to wash hands with water and soap after toilet use	Pupil	Separately for: Grade 1-3 pupils Grade 4-6 pupils	LPM: Y = Y.1
handwashin g after toilet use	Pupil washed hands with water after toilet use	Y.1 – binary variable for whether pupil was observed to wash hands with water after toilet use at school	Pupil	Separately for: Grade 1-3 pupils Grade 4-6 pupils	LPM: Y = Y.1

Table 3: Outcome Indicators for Research Question 1

³⁶ Unless otherwise stated, the independent variable of interest is treatment assignment.

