Unit	Co-variate	Metric	Hypothesized relationship to outcome
	District Number of pupils enrolled (pre- intervention)	 X.1 – categorical variable where each value category represents the school district where the school is located X.2 – continuous variable to represent the number of pupils enrolled at the elementary school prior to intervention³⁷ X.3 – index variable between 0 and 11 	 School district is associated with geographic location, which may be associated with varying levels of rurality, access to water, socio-economic status of teachers and pupils, or support received from DepEd division office. Given that school budget is partially determined by number of pupils enrolled, and that larger schools tend to be located in urban or semi-urban areas, school resources and the school pupil and teacher population may vary depending on school size. This will be estimated using information reported by principals during end-line school visits or using the data reported in DepEd's Online Monitoring System (OMS), depending on how reliably information reported by principals can be collected.
School	WinS implementatio n quality index score (pre- intervention)	composed of 11 binary indicators related to WASH conditions at the school, as reported in OMS data by principals prior to the intervention ³⁸	Higher score indicates a higher level of reported quality of WinS implementation, and may thus be associated with a higher level of handwashing infrastructure and supplies, as well as more consistent implementation of WinS program activities involving pupils, such as group handwashing and tooth- brushing.
	Nudge- enabled	X.4–binary variable for whether school is "nudge-enabled" or not "nudge-enabled"	Nudge-enabled schools are those with combinations of features that indicate they may be more conducive to nudge intervention than schools without those features. Please see Section 2.5 Recruitment of Participants (Sampling) for details of these nudge-enabling features. Because of the presence of these features, the nudge intervention may have greater impact on nudge-enabled schools than schools that are not.

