- Y_{ij} denotes the outcome variable for pupil *i* in school *j*, classified as a binary variable, as specified in Table 3.
- *T_j* denotes the treatment variable (binary variable for whether school *j* received the nudge intervention)
- \vec{X}_{2ij} represents a vector of pupil, school, and class level co-variates as specified in Table
- ε_{ij} denotes the pupil error term *i*, clustered at the school-level to reflect the fact that the treatment assignment was at the school level
- β_n denotes the coefficients determined by the regression model (β₁ is coefficient of interest)

1.d. Sub-group analysis: the impact of the nudges intervention on the outcomes of iHWWS after toilet use will be estimated using the analytic model described in sub-section 1.c, for the pooled sample and each of the two samples corresponding to grade groups (grades 1-3 and grades 4-6). The impact for these two grade groups will be compared to assess whether the effect of the treatment is different across grade groups.

In addition, within each sample, sub-group analysis will be conducted to compare the average impact of the nudges intervention by:

- pupil gender
- WinS implementation quality index score
- number of pupils
- nudge conduciveness of handwashing area

1.d.i. Treatment impact by grade group: The impact of the nudges intervention on the outcomes of iHWWS after toilet use will be estimated separately for pupils grade 1-3 and grade 4-6. To test whether the impact of the intervention on these key outcomes was statistically significantly different in the two samples, the impact estimates in the two models corresponding to the two different samples will be compared by testing the equality of the regression coefficients.³⁹

1.d.iii. Treatment impact by pupil gender: In order to compare the average effect of the intervention on the outcomes of independent handwashing after toilet use between girl and boy pupils, sub-group analysis will be conducted using the following regression:

 $Y_{ij} = \beta_0 + \beta_1 T_j + \beta_2 F_i + \beta_3 (T_j \times F_i) + \overrightarrow{\beta_4} \overrightarrow{X}_{4ij} + \varepsilon_{ij}$

Where:

- *F_i* is a dummy variable denoting whether pupil *i* is female
- \vec{X}_{4ij} represents a vector of pupil, school, and class level co-variates as specified in Table 2, excluding pupil gender
- All other regression terms are defined as they were in the previous regression specification and β₃ is the coefficient of interest.

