2.b. Indicators, unit of analysis and sample: Table 5 below provides a summary of the indicators for this research question, and the unit of analysis and sample corresponding to each indicator. These indicators are based on enumerator observations of toilet and handwashing facilities at the schools visited.

Table 5: Outcome indicators for Research Question 2

Outcome category	Outcome	Metric	Unit	Sample	Analytic model ⁴⁰ (LPM – linear probability model; OLS – ordinary least squares)
(a)	Availability of functioning handwashing facilities with soap	Y.1 – continuous variable where value represents the number of functioning handwashing facilities with soap at the school	School	All T&C schools	OLS with Y=Y.1
Availability of handwashin g facilities	Presence of functional handwashing facility with soap near toilet facility	Y.1 – binary variable for whether there is a functioning handwashing facility with water and soap inside classroom for classroom toilet facilities and within 10 meters of functioning toilet facility for block toilet facilities	Toilet facility	All toilet facilities at T&C	LPM with Y=Y.1
with water and soap	Presence of functional handwashing facility near toilet facility	Y.1 – binary variable for whether there is a functioning handwashing facility with water inside classroom for classroom toilet facilities and within 10 meters of functioning toilet facility for block toilet facilities		school	LPM with Y=Y.1

⁴⁰ Unless otherwise stated, the independent variable of interest is treatment assignment.

The analytic model used to answer research question 2. will also include the following co-variates, as they were defined in the analytic model for research question 1 (see Table 4):

• School-level variables: school district; WinS implementation quality index score (preintervention)

In addition, for outcomes for which the unit indicated in Table 5 is the toilet facility and the analytic model is LPM, the following will be included as co-variates:

- School-level variable: number of pupils enrolled at the school (pre-intervention)
- **Facility-level variable:** Location of the toilet facility observed, defined as a categorical variable where each value category represents which of following location the classroom facility is inside a classroom from grade 1-6, or outside a classroom.

2.c. Analytic model

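### The with-controls RQ1 models spend one school-level parameter per district, but no variance correction that charges for them is named; under the default clustered variance the standard error is too small

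*SAP*

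**What the plan says.** SAP section 6, Table 4 defines district as "X.1 – categorical variable where each value category represents the school district where the school is located". Enrolment (X.2), WinS score (X.3) and nudge-enabled status (X.4) are the other school-level covariates. In 1.c, a single linear probability model contains treatment and a term that "represents a vector of pupil, school, and class level co-variates as specified in Table". Its error is "clustered at the school-level to reflect the fact that the treatment assignment was at the school level". Neither a variant of the clustered variance nor a reference distribution is given.

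The note on the sample for RQ1 adds: "We will report estimates for our outcome indicators both with and without controls". Neither version is named as the deciding one.

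RQ2 carries the same covariate forward (2.b: "School-level variables: school district; WinS implementation quality index score"), and its facility-level models (2.c.i) are also clustered by school.

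The number of districts appears nowhere. Section 2.3 says only that "DepEd has identified all school districts within Zone 1-3, and several in Zone 4, as sites for the study". On the number of schools, section 2.5 says "we expanded the sample size to 132 in total, with 66 schools per arm", where 100 were needed for power.

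**The concern.** Treatment varies only between schools, so the information about its effect comes from 132 school-level units. Each district indicator, and each other school-level covariate, uses up one of them. The default clustered variance in common software corrects for the number of parameters by counting pupils, of whom there are about 3,400. It therefore treats two dozen school-level parameters as negligible. Residuals are over-fitted at school level, the standard error shrinks, and the t distribution on schools minus 1 degrees of freedom does not make up for it. Having more than 100 clusters does not help, because what matters is the number of school-level parameters relative to the number of schools.

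At stake are the p-value and confidence interval of the adjusted RQ1 effect, pooled and by grade group.

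**Working it through.** **The plan's own figure.** Inputs from section 2.5: rates 0.10 and 0.17, two-sided alpha 0.05 (sidedness assumed), power 0.80, ICC 0.1, 26 pupils per school. Two proportions need 373 pupils per arm. The design effect is 1 + (26 − 1) × 0.1 = 3.5. Schools per arm: 373 × 3.5 / 26 = 50.2, or 100.4 in total against the stated 100. The figure reproduces and is not in dispute.

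**The mechanism.** Let G be schools, N pupils, D districts and K parameters. Counting treatment, D district parameters (including the intercept), enrolment, WinS score and nudge-enabled status, K = D + 4. Take D = 20, so K = 24, with G = 132 and N = 132 × 26 = 3,432.

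- Default correction for parameters: (N − 1)/(N − K) = 3,431/3,408 = 1.007.
- School-level equivalent: (G − 1)/(G − K) = 131/108 = 1.213.
- Over-fitting shrinks the standard error by about √((G − K)/G) = √(108/132) = 0.905. The default gives back only √(132/131 × 1.007) = 1.007, so the net ratio is about 0.91.
- The test uses t on 131 degrees of freedom, critical value 1.978. Simulation gave a ratio of 0.914. Then 1.978 × 0.914 = 1.808, whose two-sided normal tail is 0.071 rather than 0.05.

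**Simulation under no effect.** Pupils were beta-binomial with a 10% rate, ICC 0.1 and 26 per school. The model had treatment, D districts, WinS score, enrolment and nudge-enabled status, and the default clustered variance with t on G − 1. Class- and pupil-level covariates were left out. Set 1 had 10,000 runs per cell; its Monte Carlo error at 5% is √(0.05 × 0.95/10,000) = 0.002. Set 2 had 6,000 runs, with assignment stratified as in section 2.6. The set 2 code matched a standard package's pupil-level clustered standard error exactly on a test data set. D is an assumption throughout.

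| D | √((132 − K)/132) | SE / true SD, set 1 | True error, 132 schools, set 1 | Same, set 2 | True error, 100 schools, set 1 |
|---|---|---|---|---|---|
| 5 (6 in set 2) | 0.965 | 0.968 | 0.059 | 0.059 | 0.064 |
| 10 | 0.945 | 0.948 | 0.061 | 0.063 | 0.068 |
| 20 | 0.905 | 0.914 | 0.075 | 0.072 | 0.085 |
| 30 | 0.862 | 0.889 | 0.087 | 0.090 | 0.094 |

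**Isolating the cause.** With the other school covariates but no district indicators, the error at 132 schools is 0.054. It rises with D from there. The model without controls stayed at 0.043-0.055 in every scenario. Grade-group models (13 pupils per school) gave 0.061 to 0.086 for 6 to 30 districts. At a 3% rate the range was 0.056 to 0.079.

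**Checking the remedy.** In set 1 at 132 schools, CR2 with t on G − K gave 0.049-0.053. A separate run of CR2 with Satterthwaite degrees of freedom gave 0.042-0.054.

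**The case against.** The strongest reply is that the SAP does not choose the default variance; it is silent. CR2 is itself a school-clustered standard error and fits the quoted sentence. That stands, so the point has to be conditional. It survives because a plan that names nothing is normally run on default software output.

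The size also rests on a district count that the SAP does not give. With 5 or 6 districts the error is about 0.059 against 0.054 with none, which is slight.

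A reader might infer that the primary RQ1 result is invalid. The documents do not support this. Estimates with and without controls are both planned, neither is ranked, and the one without controls holds its level. A material discrepancy between the two would be visible. The scale-up decision in section 2.5 also depends on rates passing 15%, not only on a p-value.

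A reader might also infer errors of 9-10% from the planned class-selection weights. Simulation gave 0.090 at 20 districts and 0.100 at 30, but with weights assumed to run from 1 to 5. The SAP gives no sizes, so these values are illustrative only.

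Nor can one say that RQ2 suffers to the same degree. Facility numbers per school, their ICC and their outcome rates are not given.

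Finally, adjusting for district is not improper merely because it was not a stratum. Table 4 gives a prognostic reason for it. The issue is how the standard error is computed.

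**Conclusion.** The point holds conditionally and is a cheap improvement. If the with-controls RQ1 models are run with the default clustered variance, the treatment standard error is about 3% too small with 5 districts, 5% with 10, 9% with 20 and 11% with 30, at 132 schools. A nominal 5% test then has a true error of about 6% for 5 to 10 districts, 7-8% for 20 and 8-9% for 30. At 100 schools it is roughly half a point to one point higher.

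These figures assume a 10% rate, ICC 0.1, 26 pupils per school, no weights and a two-sided test; the district count is the main unknown. The estimate without controls is not affected. RQ2's school-level OLS is not affected either, because its usual standard error already charges for parameters at school level. The RQ2 facility-level models share the mechanism at an unknown size.

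**What to change.** Add one sentence to section 6: for every clustered model that includes X.1, inference on treatment uses CR2 standard errors with Satterthwaite degrees of freedom, or randomisation inference that re-draws the assignment within the WinS categories, separately for nudge-enabled and other schools. It would help to state the number of districts in the sample and to say which of the two RQ1 estimates, with or without controls, decides.

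The cost is a standard software option and slightly wider confidence intervals for the adjusted estimates. No new data are needed, and the sample size is unchanged.

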1. iHWWS rates (impact evaluation, RQ1)	iHHWS after toilet use observations in classroom (treatment & control)	4 months post- implementation	Enumerators will observe whether pupils wash their hands with soap, wash without soap, or do not wash, after they have used classroom toilets. This will be used to estimate the causal impact of the nudges intervention on iHHWS rates.
2. Homogeneity in toilet and handwashing environment (impact evaluation, RQ1)	Structured facilities observations for both treatment and control (treatment & control)	4 months post- implementation	Structured observations of each facility will assess factors such as: presence of existing WASH-related informational posters, whether the handwashing area is used for other non-WASH purposes (e.g. storage, dish-washing area), whether the handwashing station has objects unrelated to handwashing ³³ , how many primary colors are present in health corner where handwashing station is present, and other factors related to visual clutter to be finetuned after piloting. These will be used to construct a measure of whether the facility is conducive to nudges, to be used in subgroup analyses.
2. Access to soap and water (impact evaluation, RQ2)	Structured facilities observations (Treatment & control)	4 months post- implementation	Structured observations of whether classroom handwashing facilities including soap and water. These will be used to estimate the causal impact of the nudges intervention on pupil access to soap.
3. Nudges implementation (process evaluation, RQ3)	Structured facilities observations (treatment)	During implementation visit but after nudge installations are completed	Structured observations of facility after implementation, to assess presence and condition of nudges in toilet and/or handwashing station. These will be used to assess if installation proceeded as intended.
4. Nudges implementation (process evaluation, RQ3)	Structured facilities observations (treatment)	4 months post- implementation	Structured observations of presence and condition of nudges in toilets and/or handwashing facilities. These will be used to assess if installed nudges functioned and lasted as expected.

³³ A concern is that handwashing areas both across and within schools may differ in terms of how conducive they are to nudges; more cluttered and busy environments may dilute the impact of nudges.

Pre-analysis plan [DRAFT] | January 20, 2020

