5. ETHICAL CONSIDERATIONS

ETHICAL CLEARANCE

Given the nature of the evaluation activities and the relatively low sensitivity of the survey questions, the study poses little risk to participants. IDinsight will apply for ethical clearance for the research through a research ethics committee accredited by the Philippine Health Research Ethics Board (PHREB). We will apply for ethical clearance for the study in October 2019, after we have finalized the evaluation design and prepared all the necessary documentation.

RECRUITMENT STRATEGY

DepEd national and division staff were consulted in the design of the nudges and evaluation. DepEd divisions and treatment schools in Zamboanga del Norte will be provided information of the details of the nudges and installation prior to implementation. This will be done either in-person or via phone by either IDinsight staff or supporting members of DepEd.

No additional implementation activities will be conducted and no supplies will be distributed to schools or pupils as part of the evaluation. In addition, WinS programs have previously been implemented in these school divisions with support from UNICEF, and all participating schools (both treatment and control) may thus be familiar with both WinS programs and UNICEF.

INFORMED CONSENT & ASSENT

Prior to visiting schools, letters from DepEd divisions will be obtained, and will be presented to principals at all schools visited to describe the research aims and activities, and confirm DepEd authorization. Upon first arrival at each school, permission will be obtained from the principal prior to collecting any observation or survey data.

Once principal permission is granted, teachers of classes selected for observation or pupil surveys will be sensitized about the study and the data collection activities.

CONFIDENTIALITY

All pupil observations will be conducted at the school. The observations will be conducted inside the pupils' classroom or at the group handwashing station, and we will not collect uniquely identifiable information about pupils.

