Class	Number of pupils in the classroom	X.5 – continuous variable where value represents the number of pupils present in the classroom during the observation period	Classroom size may be associated with school resources and teacher quality or attention, which may influence pupil opportunity and incentives to wash hands with soap. Further, if handwashing with soap after toilet use is considered to be a norm (or habit) that the nudges remind pupils of, and if the class is considered as the primary 'social unit' for this norm, the number of pupils in this social unit may influence the likelihood of the norm arising and persisting.

Table 4: Control Variables for Research Question 1

³⁷ This variable may be converted to an ordinal variable to mitigate random error due to imprecision in the number of pupils reported.

³⁸ See Table 7 in the *Sampling* section of the evaluation design document for a description of 11 indicators an additional information on the online monitoring system (OMS) Evaluation Design Document

Pre-analysis plan [DRAFT] | January 20, 2020

	Nudge- conducive	X.6 - Binary variable indicating whether the handwashing area location near/in the classroom is "nudge conducive"	Nudge-conducive handwashing areas are those with combinations of features that indicate they may be more conducive to nudge intervention than handwashing areas without those features. Please see Section 3.2 Data Collection Activities for details of these nudge-conducive features. The nudge intervention may have greater impact for nudge-conducive handwashing areas than non-nudge conducive areas.
Unit	Co-variate	Metric	Hypothesized relationship to outcome
Pupil	Gender	X.7 – binary variable for whether pupil observed is female	Traditional gender roles tend to involve more tasks that may require handwashing for girls than boys, such as cooking or cleaning, and may thus facilitate building handwashing habits among girls.
	Grade	X.8 – categorical variable where each	The behavioral nudges targeted at changing pupil behavior may be more engaging and/or effectively

1.c. Analytic model

Specification for LPM: The effect of the treatment on the outcome variables listed in **Error! R** eference source not found. for which the analytic model indicated is the Linear Probability Model will be measured by conducting the following regression:

$$Y_{ij} = \beta_0 + \beta_1 T_j + \overrightarrow{\beta_2} \vec{X}_{2ij} + \varepsilon_{ij}$$

Where:

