 $^{^{\}rm 39}$ Observations in which the student grade was unknown will be excluded.

Pre-analysis plan [DRAFT] | January 20, 2020

1.d.iv. Treatment impact by WinS implementation quality index score: In order to compare the average effect of the nudges intervention on the outcome of independent handwashing after toilet use across different levels of WinS implementation quality, sub-group analysis will be conducted using the following regression:

$$Y_{ij} = \beta_0 + \beta_1 T_j + \beta_2 W_j + \beta_3 (T_j \times W_j) + \overrightarrow{\beta_4} \overrightarrow{X}_{4ij} + \varepsilon_{ij}$$

Where:

- *W_j* is an ordinal variable between 0 and 11 denoting the WinS implementation quality index score for school *j*
- \vec{X}_{4ij} represents a vector of pupil, school, and class level co-variates as specified in Table 2, excluding WinS implementation quality index score
- All other regression terms are defined as they were in the previous regression specification and β₃ is the coefficient of interest.

1.d.v. Treatment impact by nudge conduciveness: In order to compare the average effect of the nudges intervention on the outcome of independent handwashing after toilet use depending on the context's conduciveness to nudges, sub-group analysis will be conducted using the following regression:

Where:

$$Y_{ij} = \beta_0 + \beta_1 T_j + \beta_2 W_j + \beta_3 (T_j \times N_i) + \beta_4 X_{4ij} + \varepsilon_{ij}$$

- N_i will be a binary variable (to be constructed after seeing the distribution) =1 if the pupil
 was exposed to a nudge-conducive handwashing environment at the time of toiet use and
 =0 if not
- \vec{X}_{4ij} represents a vector of pupil, school, and class level co-variates as specified in Table 2, excluding WinS implementation quality index score
- All other regression terms are defined as they were in the previous regression specification and β₃ is the coefficient of interest.

1.e. Presentation of results: a regression table will be included for each specification to describe the correlation between key indicators of interest and co-variates. Data visualizations describing the level of the outcomes variables in the treatment and control group may also be included.

RESEARCH QUESTION 2

2.a Research question 2: What is the causal impact of the behavioral nudge intervention on pupil access to handwashing facilities with soap and water?

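### The nudge-conduciveness interaction model (SAP Section 6, 1.d.v) prints the WinS score where the moderator's main effect belongs, so any version without covariates would have no conduciveness main effect

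*SAP*

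**What the plan says.** SAP Section 6, 1.d.v compares the effect of the nudges between conducive and other handwashing environments. After the intercept and the treatment term, its equation has "\beta_2 W_j + \beta_3 (T_j \times N_i"), then the covariate vector X₄ and the error. β₃ is named as the coefficient of interest.

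X₄ "represents a vector of pupil, school, and class level co-variates as specified in Table 2, excluding WinS implementation quality index score". The same line appears under 1.d.iv, where the WinS score is the moderator.

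N is a binary variable, "to be constructed after seeing the distribution", equal to 1 if the pupil "was exposed to a nudge-conducive handwashing environment at the time of toiet use". Table 4 separately lists a covariate X.6: "Binary variable indicating whether the handwashing area location near/in the classroom is" nudge conducive. X.6 refers the reader to Section 3.2, which says of the facility observations: "These will be used to construct a measure of whether the facility is conducive to nudges, to be used in subgroup analyses".

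Under 1.b, the plan says that RQ1 outcome estimates will be shown in adjusted and unadjusted form. Table 6 puts this test with three other subgroup tests in one family of four for the Holm-Bonferroni correction.

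**The concern.** An interaction coefficient measures a difference in treatment effects only if the moderator also has a main effect in the model. Without one, the interaction term must also carry any difference in handwashing between conducive and other areas that exists without nudges. As printed, 1.d.v has no explicit N term. Whether the model is sound then depends on X.6 being present in X₄ and being the same variable as N, and the plan states neither.

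This subgroup question matters to the plan. Section 2.6 names facility-level clutteredness as the effect modifier of interest, and Section 4 offers modelling it as one of two answers to a listed technical risk.

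**Working it through.** **Step 1. Compare the five printed interaction models.**

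| Model | Main effect | Interaction | Removed from X₄ |
|---|---|---|---|
| 1.d.iii gender | F | T × F | gender |
| 1.d.iv WinS | W | T × W | WinS score |
| 1.d.v conduciveness | **W** | T × **N** | **WinS score** |
| 2.d.i toilet location | L | T × L | location |
| 2.d.ii WinS (RQ2) | W | T × W | WinS score |

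Four models use one variable in all three places. Only 1.d.v does not, and its W and exclusion line match 1.d.iv. That they were carried over is an inference, but the pattern supports it strongly.

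**Step 2. Version with covariates.** The pointer to Table 2 leads to the data collection table, which lists no covariates. Table 4 does, and 2.b cites Table 4 for the RQ1 covariates. Read that way, X.6 is not removed and stays in X₄, while W enters once, outside X₄. If X.6 is N, the model contains T, N and T × N, and β₃ is the true interaction. The bias is zero.

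**Step 3. Version without covariates.** Dropping X₄ from the printed equation leaves T, W and T × N. Suppose the truth is

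Y = p₀ + τT + dN + gTN,

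where d is the gap between conducive and other areas without nudges and g is the true interaction. Let s be the conducive share among controls, and take W as unrelated to N (if they are related, W absorbs part of the gap).

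- All controls share one fitted mean: p₀ + ds.
- Treated, N = 0: p₀ + τ.
- Treated, N = 1: p₀ + τ + d + g.

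Hence β₁ = (p₀ + τ) − (p₀ + ds) = τ − ds, and β₃ = (p₀ + τ + d + g) − (p₀ + τ) = g + d. The interaction estimate takes in 100% of d. The four sister models do not have this problem, because their moderator stays in the equation when X₄ is dropped.

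**Step 4. Illustration.** The plan gives no figure for this subgroup analysis, so there is none to reproduce. From Section 2.5, take a control rate of 10% and an effect of 7 percentage points (pp). Assume s = 0.5, g = 0 and d = +5 pp. Control rates are then 12.5% (conducive) and 7.5% (other), and treated rates are 19.5% and 14.5%.

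- Without N: β₁ = 14.5 − 10 = 4.5 pp; β₃ = 19.5 − 14.5 = 5 pp.
- With N: β₁ = 14.5 − 7.5 = 7 pp; β₃ = (19.5 − 14.5) − (12.5 − 7.5) = 0.

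Over a range of assumed d, with true β₁ = 7 and true β₃ = 0:

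| d (pp) | −5 | −3 | 0 | +3 | +5 |
|---|---|---|---|---|---|
| β₃ without N | −5 | −3 | 0 | +3 | +5 |
| β₁ without N = 7 − 0.5d | 9.5 | 8.5 | 7 | 5.5 | 4.5 |

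The error can also hide a real effect: g = +5 with d = −5 gives β₃ = 0. These values of d and s are assumptions, not features of the plan.

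**The case against.** The strongest reply is that this is a notation slip in a document marked as a draft. X.6 is not excluded, so the main effect is already in the covariate vector and no adjusted estimate changes. That stands for the version with covariates.

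A second reply is that the promise of unadjusted results in 1.b concerns the outcome indicators, that every subgroup equation is printed with X₄, and that no unadjusted interaction model is described. This stands in part. The text does not say that the promise reaches 1.d.v, but nothing rules it out, so the point is conditional.

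A reader might go further and infer that X.6 and N are different variables, since one describes an area and the other a pupil's exposure, and that β₃ is therefore biased even with covariates. Section 5 does allow observation inside the classroom "or at the group handwashing station". The documents do not support that inference. Section 2.3 brings in group stations for classrooms that lack their own facility: there, "the intervention will also be implemented at group handwashing facilities that are outside but close to these classrooms within the schools". They replace the missing facility and are not described as a second one for the same class. X.6 already covers areas near as well as in the classroom. Section 3.2 describes one measure, and the 1.d subgroup list and Table 6 attach conduciveness to the handwashing area, as X.6 does. Even if the two variables differed, β₃ would be unbiased if the ordinary gap followed X.6.

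**Conclusion.** The 1.d.v equation and its exclusion line are wrong as printed. On the likely reading, the consequence with covariates is nil. In a version without covariates, β₃ is off by the full gap d. Its sign is unknown and its size is not given in the SAP; the bias is zero if d is zero. That result assumes that W is unrelated to N and that the unadjusted reporting in 1.b reaches this model.

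The Holm correction would not protect against this, because it controls multiplicity and not a shifted estimate. The issue is confined to one secondary subgroup test out of four. A reader should not infer that the main RQ1 estimate is affected: the 1.c model contains no interaction. Severity is minor. The slip itself is certain, and its effect on results is conditional.

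**What to change.** In 1.d.v, print

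Y_ij = β₀ + β₁T_j + β₂N_i + β₃(T_j × N_i) + β₄X_4ij + ε_ij.

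Define X₄ there as the Table 4 covariates excluding X.6 and keeping the WinS score. Change the Table 2 pointer to Table 4, here and in 1.d.iii and 1.d.iv, which carry the same pointer. State that N is X.6, with one definition and one cut-off. Add that the N main effect stays in any version reported without the other covariates.

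The cost is one equation, one exclusion line, one table reference and one definition. No extra data are needed, and the result follows the template of the plan's other interaction models.
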